Interested patients will be consented and if eligible, baselined at their surgical consult visit or before their pre-op appointment. Participants who have absolute or relative contraindications to gabapentin will be excluded from participation in the study through inclusion/exclusion criteria. This visit may occur up to 3 months before their surgery. Participants will be screened for cognitive impairment by the Mini-Cognitive Assessment, and those who score 2 or less will be considered screen failures. Participants will also complete a standardized and validated symptom bother (PFIQ-sf7) and QoL questionnaires (PFDI-sf20), as well as the standardized and validated PROMIS pain interference, pain intensity, and global mental and physical health questionnaires.

Source data collected as part of routine clinical care may be used to complete CRFs as long as the window between prior data collection and the baseline visit does not exceed 18 months. This includes previously performed POP-Q exams as well as previously collected questionnaires.

- Informed consent
- Inclusion/Exclusion Form
- Baseline form (Demographics, Medical & Surgical History, pain/analgesic med use, POP-Q exam record)
- Mini-Cognitive Assessment
- PFIQ-sf7, PFDI-sf20, PROMIS questionnaires

Randomization:

The randomization table will be given to IDS who will implement randomization for the study and provide the study drug that will be given to patients before their surgery. Randomization will be done by site – Hillsborough and Rex, in a 1:1 ratio and in blocks of 4.

Surgery:

Surgical data will be collected on a Surgical Procedures Form and include items listed below.

- American Society of Anesthesiologists (ASA) grade
- Concomitant procedures performed
- Estimated blood loss (EBL)
- Intraoperative complications
- Voiding trial results

Follow-Up Procedures:

- Daily for 2 weeks after discharge: Patients will complete a Study Drug-Pain Med Count Form and Surgical Pain Scale ratings every day for the first 2 weeks after discharge.
- 2-3 days after discharge: We will call patients 2-3 days after discharge to assess for any AEs and remind pts to dose escalate. We will use the NIH Common Terminology of Criteria for Adverse Events version 4.0 (CTCAE) to determine AE severity/grade.

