- Week 1 and Week 2 calls: At Week 1 and Week 2 we will call patients to administer the PROMIS questionnaires. We will also remind patients to complete the Study Drug-Pain Med Count Form and Surgical Pain Scale, and will review any potential AEs.
- Week 3, 4, 5: Patients will complete the PROMIS questionnaires, as well as a Pain Med Count Form and Surgical Pain Scale at the end of week 3, 4, and 5 post-operatively.

Week 6 Visit:

Patients will return to clinic for a postoperative visit around week 6, in which all of the assessments listed in the table below will be performed. Patients will again complete the symptom bother (PFIQ-sf7) and QoL questionnaires (PFDI-sf20), as well as the PROMIS pain interference, pain intensity, and global mental and physical health questionnaires. In addition, we will assess for any AEs or post-operative complications that may have occurred since discharge, as well as current pain/analgesic med use.

- Week 6 form (pain/analgesic med use, post-op complications)
- PFIQ-SF7, PFDI-SF20, PROMIS questionnaires
- Surgical Pain Scale

Table 1. Schedule of Assessments

| Schedule of Assessments | # ?s | Baseline | 2-3 day post-op call | Daily for 2 wks post-op (completed at home) | Wk 1 call | Wk 2 call | Every wk Wk 3-5 (completed at home) | 6 Wk visit |
|--|------|----------|----------------------|---|-----------|-----------|-------------------------------------|------------|
| PFDI-20 | 20 | X | | | | | | X |
| PFIQ-7 | 7 | X | | | | | | X |
| PROMIS pain interference/intensity | 7 | X | | | X | X | X | X |
| PROMIS depression/anxiety short forms | 8 | X | | | | | | X |
| PROMIS global mental/physical health | 4 | X | | | X | X | X | X |
| Medical/Surgical history | | X | | | | | | |
| Pain medications assessment | | X | | | | | X | X |
| Study Drug-Pain Med Count Form | | | | X | X | X | | |
| Surgical pain scale (SPS) + gluteal pain | 6 | | | X | X | X | X | X |
| Adverse events assessment | | | X | | X | X | | X |
| Total # of questions at each visit | | 46 | | 6 | 18 | 18 | 18 | 52 |

Outcome measures

Primary Outcome

Overall post-operative pain will be measured by item 2 of the surgical pain scale (SPS) on post-op day 7. This item measures the average pain felt during normal activity in the last 24 hours on a scale of 1-10.

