(SPS validated by OPTIMAL study and in older women; OPTIMAL was a multicenter NIH sponsored Pelvic Floor Disorders Network study comparing SSLF to uterosacral ligament suspension surgery for POP).(11, 12)

Secondary outcomes:

1. Gluteal pain on post-op day 7 will be measured by a numeric rating scale like that used in the SPS (0-10)
2. Other pain scale items such as SPS pain at rest, pain w/normal activity (primary outcome), unpleasantness of worst pain sensation, gluteal pain at rest and gluteal pain w/normal activity on POD#7
3. Daily Narcotic pain medication use for 2 weeks post-op and then through week 6 post-op

DATA ANALYSIS

Sample size

OPTIMAL study found that SPS score for pain with normal activity

- Wk 2 = mean 2.9 (2.6 SD) median 2 (1-4 IQR) range: 0-10
- Pain is likely to be higher at Wk 1
- 17 per group to detect 2.5 difference in SPS, SD 2.6 with alpha 5%, power 80%
- **If 20% drop out, need 19 per group so 38 total at min**

Statistical Analysis Plan

- Bivariate analyses to compare our two cohorts: Student's t-test, chi-square/Fisher's exact and Mann-Whitney U for continuous variables, categorical variables and ordinal/skewed data respectively.

Primary outcome

- We will compare pain with normal activity scores on POD#7 using Student's t-test or Mann-Whitney U as appropriate

Secondary outcomes

- We will use Student's t-test or Mann-Whitney U as appropriate to compare gluteal pain scores on POD#7
- We will compare total narcotic use in average morphine milliequivalents per day during the first two weeks using Student's t-test or Mann-Whitney U as appropriate
 - Convert different narcotics into morphine equivalents and add up total narcotic use as needed
 - Compare with t-test if parametric vs Mann-Whitney U if nonparametric
 - Perform a linear regression analysis and adjust for baseline pain medication usage in order to account for the fact that baseline pain medication usage may impact postoperative narcotic use. We can also adjust for postoperative non-narcotic pain medication.

References

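### The primary test uses the POD 7 score alone and by default drops patients without it, although daily ratings of the same item could recover part of what is lost

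*Combined protocol and SAP*

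**What the plan says.** The Outcome measures section fixes a single-day endpoint: "Overall post-operative pain will be measured by item 2 of the surgical pain scale (SPS) on post-op day 7". Under Statistical Analysis Plan, the only method for it is: "We will compare pain with normal activity scores on POD#7 using Student's t-test or Mann-Whitney U as appropriate". The section names no analysis set, missing-data rule, repeated-measures model or sensitivity analysis. Its one regression concerns narcotic use.

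The same item is collected far more often than it is used. Follow-Up Procedures asks for "Surgical Pain Scale ratings every day for the first 2 weeks after discharge", and no planned pain comparison uses any day but POD 7. For the Week 1 and Week 2 calls the text says: "We will also remind patients to complete the Study Drug-Pain Med Count Form and Surgical Pain Scale". Table 1, however, marks the SPS as an assessment at both calls.

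Loss appears only under Sample size: "If 20% drop out, need 19 per group so 38 total at min". On allocation, the Randomization paragraph says: "Randomization will be done by site – Hillsborough and Rex, in a 1:1 ratio and in blocks of 4". The primary test has no site term.

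**The concern.** A t-test or Mann-Whitney test can use only patients who have a POD 7 score. Dropping the others gives an unbiased comparison only if the absence of that entry is unrelated to pain. Scores are self-recorded at home, so patients in more pain might skip the diary. If so, more high scores would be lost on placebo than on gabapentin, and the difference would be understated. In a trial of 38, each lost patient also costs noticeable precision. Ratings from the preceding days would carry information about the missing score, but the plan does not use them. With no rule written down, the handling of blanks could be settled after the data are seen.

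**Working it through.** **Inputs from the plan.** Difference 2.5, SD 2.6, alpha 5% (taken as two-sided, which reproduces the plan's figure), power 80%, 19 per arm, 20% loss, 1:1 allocation.

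**Assumptions (not in the documents).** Correlation of 0.5 to 0.8 between POD 7 and the POD 5 and 6 ratings; how much of the 20% falls at POD 7; why entries are missing; how many patients without POD 7 have POD 5 and 6 entries.

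**1. The plan's figure.** The plan states "17 per group to detect 2.5 difference in SPS, SD 2.6 with alpha 5%, power 80" per cent. n = 2 × (1.960 + 0.842)² × (2.6/2.5)² = 2 × 7.849 × 1.0816 = 16.98, so 17 per arm. It reproduces under the normal approximation; the exact t-test needs 18.

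**2. If all 20% is lost at POD 7.** 19 × 0.8 = 15.2 per arm. Power = Φ(2.5/(2.6√(2/n)) − 1.960) = Φ(2.651 − 1.960) = 75.5%. The exact t-test with 15 per arm gives 72.0%. With no loss, 19 per arm gives 84.2% (exact 82.2%).

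**3. The part due to inflation.** 17/(1 − 0.2) = 21.25, so 22 per arm. Then 22 × 0.8 = 17.6, and power = Φ(2.852 − 1.960) = 81% by the same approximation. The error in reaching 19 is separate, and it explains the drop from about 81% to 75.5%.

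**4. Approximate gain from earlier ratings.** Variance of an arm mean = SD² × [(1 − R²)/n_obs + R²/(n_obs + k)]. Here R is the correlation of POD 7 with the earlier ratings, n_obs = 15.2, and k is the number with earlier ratings but no POD 7 score.

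| R | Effective n, k = 3.8 | Power, k = 3.8 | Power, k = 1.9 |
|---|---|---|---|
| 0.5 | 16.0 | 77.6% | 76.7% |
| 0.7 | 16.85 | 79.7% | 77.8% |
| 0.8 | 17.43 | 81.0% | 78.5% |

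The comparator is 75.5%.

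**5. Simulation at the planned size.** 19 per arm, normal scores, POD 5 and 6 always available, 2,500 trials per scenario, no site or PROMIS term. Each cell gives the complete-case t-test, then the likelihood estimate using POD 5 and 6.

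| Correlation | Random 20% loss: power | Loss rising with POD 5–6 pain (about 18%): effect | Same: power |
|---|---|---|---|
| 0.5 | 72 → 73% | 2.32 → 2.49 | 69 → 74% |
| 0.7 | 73 → 76% | 2.25 → 2.49 | 66 → 76% |
| 0.8 | 72 → 78% | 2.25 → 2.51 | 67 → 78% |

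Type I error of the likelihood estimate was 3.9 to 4.7%. Multiple imputation of POD 7 from arm and mean POD 5–6 score agreed: random-loss power 71.5 → 72.1%, 71.3 → 75.6% and 72.0 → 77.7%; pain-related effect 2.30 → 2.47, 2.29 → 2.52 and 2.23 → 2.51. With scores rounded and clipped to 0–10, pain-related power was 65–68% against 74–77%.

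**6. Where the gain shrinks.** At correlation 0.7:
- 5% missing: power 79 → 80% under random loss; effect 2.45 → 2.50 if pain-related.
- 10% missing: power 78 → 79% under random loss; if pain-related, power 77 → 80% and effect 2.40 → 2.50.
- Half of those missing POD 7 also lack POD 5–6, pain-related loss: effect 2.29 → 2.42, power 68 → 73%.

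Under 20% random loss with half lacking POD 5–6, the gain is about 2 to 2.5 points. For a patient with no diary at all, nothing is recovered.

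**The case against.** A two-sample test at one pre-specified day is simple and legitimate in a trial of about 38. The case against replacing it has real force.

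- **The 20% is a contingency without a date.** Follow-up runs to week 6, and loss by POD 7 may be much lower. This stands, and it is why the gain may be only 0 to 2 points.
- **Collection near POD 7 is already reinforced.** Table 1 marks the SPS at the Week 1 call. The 7 + 4 PROMIS questions plus 6 SPS questions make 17 of the 18 listed there, so the SPS appears to be counted. The text of the call promises only a reminder, so the two places need reconciling. If scores are taken by phone, those still missing may also lack POD 5 and 6.
- **Much of the power deficit belongs to the inflation error.** This stands. With 22 per arm, the model would mainly address bias and precision.
- **The bias is hypothetical.** The documents do not indicate pain-related diary loss, and the tabulated mechanism is conservative for a superiority claim. If missingness depends on the unseen POD 7 score itself, the model does not remove the bias.
- **Scores are bounded and skewed.** The planning data are "Wk 2 = mean 2.9 (2.6 SD) median 2 (1-4 IQR) range: 0-10". The rounded and clipped simulation went the same way, but the full model with site and PROMIS terms was not simulated.

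The size of three-day modelling is not a strong objection: an unstructured covariance for three days has six parameters, and type I error held. None of these points supplies a reason to leave the recorded POD 5 and 6 ratings unused.

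**Conclusion.** The point holds as an avoidable weakness of modest and uncertain size. The planned test by default discards patients without a POD 7 score and leaves unused ratings that the trial already collects. The size figures rest on assumed correlations of 0.5 to 0.8, available POD 5 and 6 entries and, for removal of bias, missingness explained by recorded ratings.

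A reader might infer three stronger things that the documents do not support:
- That the plan expects 20% of POD 7 scores to be missing. It gives a sample-size condition with no time point.
- That the primary estimate will be biased. No mechanism of missingness is documented.
- That a repeated-measures model would make good the planned power. At 19 per arm with 20% loss, the tabulated simulations reach 73 to 78%, and the inflation needs its own correction.

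That patients without a score are dropped is itself the default of the named tests combined with the plan's silence, not a stated rule.

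**What to change.** Pre-specify as primary a likelihood-based repeated-measures model of SPS item 2 on POD 5, 6 and 7. Use categorical day, treatment, treatment-by-day, site, and baseline PROMIS pain intensity where available, with unstructured covariance and Kenward-Roger degrees of freedom. Report the POD 7 treatment difference, so the question is unchanged. Include every randomised patient with at least one of the three ratings.

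Keep the two-sample POD 7 test (t or Mann-Whitney) as a sensitivity analysis, which also covers the skewed scores, and add an analysis under missing-not-at-random assumptions. Reconcile the Week 1 call text with Table 1 so that item 2 is recorded by phone when the POD 7 diary entry is absent. Correct the dropout inflation separately.

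The model and call changes cost SAP wording and a little programming, with no new visits; correcting the inflation would add patients (22 rather than 19 per arm). The downsides are that the model assumes the observed ratings explain missingness, it treats a bounded, skewed score as roughly normal, and a few scores would come by phone. The PROMIS covariate may be weak for some patients, because the Baseline visit section accepts routine-care questionnaires up to 18 months old.

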Given the risk of overall postoperative pain and neuropathic gluteal pain after a SSLF for POP and the evidence that perioperative gabapentin may decrease acute pain and neuropathic pain, we propose a novel randomized trial to compare perioperative gabapentin versus placebo on postoperative pain after a vaginal SSLF surgery.

STUDY AIMS

Primary aim: To assess the impact of gabapentin versus placebo on postoperative pain on postoperative day (POD) #7 after a vaginal sacrospinous ligament suspension for apical pelvic organ prolapse.

We hypothesize that a one week course of post-operative gabapentin will decrease overall post-operative pain on POD #7 as compared to placebo.

Secondary aims:

- To assess the impact of gabapentin versus placebo on gluteal postoperative pain on POD#7.
We hypothesize that a one-week course of gabapentin will decrease overall gluteal pain as compared to placebo on POD#7.
- To compare narcotic use during the first two weeks between the gabapentin and the placebo group.
We hypothesize that there will be lower narcotic use in the gabapentin compared to placebo group

STUDY DESIGN & METHODS

This study is a double-blinded randomized controlled trial comparing the impact of 2 weeks of gabapentin vs placebo on post-operative pain.

Study Population

Inclusion criteria:

- Women age 18+
- English-speaking
- Planning to undergo a vaginal SSLF

Exclusion criteria:

- Pregnant or planning to become pregnant during study participation
- Prior or concurrent vaginal mesh surgery for POP (midurethral sling is not an exclusion)
- Planning a concurrent TVH, colpocleisis (total vaginectomy or LeFort colpocleisis), mesh excision, anal sphincteroplasty, fistula repair, or urethral diverticulectomy
- Cognitive impairment (indicated by a score of 0-2 on Mini-Cog)
- Currently taking gabapentin or pregabalin (Lyrica) or previous intolerance to gabapentin or pregabalin
- Daily use of narcotics for \geq 2 months
- Acute or chronic renal failure based on past medical history (PMH) or glomerular filtration rate (GFR) < 30ml/min (see meds info below)
- Severe uncontrolled depression or bipolar disease based on PMH
- Fall risk if history of fall in last year or current use of cane/walker
- Joint procedure with other service (ie colorectal surgery/gyn onc)

Intervention

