Participants undergoing SSLF will be randomized to receive either 2 weeks of post-op gabapentin or placebo, starting with 300mg qhs for the first 3 days post-op, then on day 4 patients will dose escalate to 300mg bid for 11 additional days for a total of 2 weeks.

- UNC IDS will provide active and placebo capsules (300mg dose), 1 x 3d postop (subtotal 3), 2 x 11d postop (subtotal 22) = 25 total
- We will use NIH Common Terminology of Criteria for Adverse Events version 4.0 (CTCAE) criteria (15)
- Specific AEs to assess:
 - Dizziness ~ 15%
 - Sedation/somnolence ~ 15%
 - Nystagmus ~ 8% (involuntary movements of the eyeballs)
 - Ataxia ~ 3% (lack of coordination of muscle movements)

Patient incentives

- 6 wk visit - \$50

Data and Safety Management

Study data will be entered into and stored in a secure REDCap database hosted by UNC-CH.

Adverse events will be monitored and assessed using the NIH Common Terminology of Criteria for Adverse Events version 4.0 (CTCAE) criteria, which grades each adverse events from Grade 1 (mild), Grade 2 (moderate), Grade 3 (severe), Grade 4 (life threatening), Grade 5 (death related to AE). (15)

- The PI will be responsible for assessing each AE in terms of whether the AE is expected and/or attributable to the study drug along with the severity of the AE using the CTCAE ratings

- Serious AEs will be reported to the IRB per IRB UPIRSO guidelines
- Specific AEs to assess:
 - Dizziness ~ 15%
 - Sedation/somnolence ~ 15%
 - Nystagmus ~ 8% (involuntary movements of the eyeballs)
 - Ataxia ~ 3% (lack of coordination of muscle movements)

For example, dizziness is rated/described below in the NCI CTCAE(10) Table.

| Nervous system disorders | | | | | |
|--|--|---|--|---|---|
| Adverse Event | Grade | | | | |
| | 1 | 2 | 3 | 4 | 5 |
| Dizziness | Mild unsteadiness or sensation of movement | Moderate unsteadiness or sensation of movement; limiting instrumental ADL | Severe unsteadiness or sensation of movement; limiting self care ADL | - | - |
| Definition: A disorder characterized by a disturbing sensation of lightheadedness, unsteadiness, giddiness, spinning or rocking. | | | | | |

Schedule of Assessments (see Table 1.)

Baseline visit:

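### The optional adjustment of narcotic use for postoperative non-narcotic analgesics conditions on a post-randomisation variable and can bias the treatment effect

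*Combined protocol and SAP*

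**What the plan says.** The second secondary aim is "To compare narcotic use during the first two weeks between the gabapentin and the placebo group". Under Secondary outcomes, the Statistical Analysis Plan gives the main analysis: "We will compare total narcotic use in average morphine milliequivalents per day during the first two weeks using Student's t-test or Mann-Whitney U as appropriate". Beneath it comes a regression: "Perform a linear regression analysis and adjust for baseline pain medication usage". The plan justifies that covariate on the ground that prior use may influence later narcotic use. The next sentence is "We can also adjust for postoperative non-narcotic pain medication". It carries no reason, no condition for use, no estimand and no exploratory or sensitivity label, and nothing elsewhere in the document limits it.

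Three other places fix the timing:

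- **Randomization:** the pharmacy service is to implement the allocation and "provide the study drug that will be given to patients before their surgery".
- **Intervention:** "Participants undergoing SSLF will be randomized to receive either 2 weeks of post-op gabapentin or placebo".
- **Follow-Up Procedures:** "Patients will complete a Study Drug-Pain Med Count Form and Surgical Pain Scale ratings every day for the first 2 weeks after discharge".

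**The concern.** Adjusting for a baseline variable leaves the randomised comparison intact. Adjusting for something that happens after allocation, and that treatment may alter, does not. Postoperative non-narcotic use falls in essentially the same weeks as the treatment and the outcome. The trial's own hypothesis supplies a route from treatment to covariate: "We hypothesize that a one week course of post-operative gabapentin will decrease overall post-operative pain on POD #7 as compared to placebo". Patients in less pain may take fewer analgesics of every kind.

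Holding non-narcotic use fixed then does two things. It removes any part of the narcotic effect that operates through non-narcotic use. It also compares patients who match on that use but may differ in underlying pain. The resulting coefficient answers a different question from the aim, yet nothing in the plan prevents it from being reported as the effect of gabapentin on narcotic use.

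**Working it through.** **Plan figures.** The plan states no figure for the narcotic-use regression. Its sample size concerns the primary pain score and reproduces by the normal approximation, two-sided: 2 × (1.96 + 0.84)² × (2.6/2.5)² = 16.96, so 17 per group. It plays no part in this point except as a scale for precision.

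**General result.** Let δ be the effect of arm on non-narcotic use and γ the within-arm slope of narcotic use on non-narcotic use. In a linear model:

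adjusted effect − unadjusted effect = −γ × δ

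This is zero only if γ or δ is zero. The documents give neither quantity, so every input below is an assumption.

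**Illustration 1: pain drives both kinds of use.** Assume that gabapentin lowers pain by 0.5 SD, pain has a loading of 0.6 on narcotic use, and non-narcotic use correlates ρ with pain within arm (unit within-arm variances). The total effect on narcotic use is −0.5 × 0.6 = −0.30 SD. Then δ = −0.5ρ and γ = 0.6ρ, so the adjusted effect is −0.30 + 0.30ρ² and the share removed is ρ². If half of the −0.30 is direct, the pain loading is 0.3, and the share removed halves.

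| ρ | Adjusted effect, all through pain | Share removed, all through pain | Share removed, half direct |
|---|---|---|---|
| 0.3 | −0.273 | 9% | 4.5% |
| 0.5 | −0.225 | 25% | 12.5% |
| 0.7 | −0.153 | 49% | 24.5% |

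Simulating 2,000,000 patients gave 8.8%, 24.9% and 49.2% for full mediation and 4.4%, 12.3% and 24.9% for half. In this model the share is zero if none of the effect runs through pain, but only because the model has no direct path from non-narcotic to narcotic use.

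The direction can reverse. With ρ = 0.5 and a further +0.5 SD arm effect on non-narcotic use, δ = −0.25 + 0.5 = +0.25 and γ = 0.3. The adjusted effect is −0.30 − 0.3 × 0.25 = −0.375, which is 25% too large.

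**Illustration 2: adding an opioid-sparing path.** Let a be the arm effect on non-narcotic use, b the effect of non-narcotic on narcotic use, and c and d the effects of underlying pain propensity on non-narcotic and narcotic use. Non-narcotic use has unit within-arm variance. The bias is −a(b + cd).

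| Assumed values | Total | Adjusted | Bias |
|---|---|---|---|
| a = 0 | −0.50 | −0.50 | 0 |
| a = −0.5, b = −0.3, c = d = 0 | −0.35 | −0.50 | −0.15 (benefit overstated) |
| a = −0.5, b = 0, c = d = 0.5 | −0.50 | −0.375 | +0.125 (understated) |
| a = −0.8, b = 0, c = d = 0.7 | −0.50 | −0.108 | +0.392 (understated) |
| a = −0.5, b = −0.3, c = d = 0.5 | −0.35 | −0.375 | −0.025 (nearly cancels) |
| a = −0.5, b = 0, c = d = 0.5, no true effect | 0 | +0.125 | +0.125 (spurious) |

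Simulation agreed with each bias to within 0.002.

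**Scale.** The standard error of a two-arm difference is √(2/19) = 0.32 SD at 19 per group, or √(2/17) = 0.34 SD at 17. The shifts in the table for illustration 1 under full mediation run from 0.30 × 0.09 = 0.027 to 0.30 × 0.49 = 0.147 SD, less than half of one standard error.

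**The case against.** The strongest reply is that the plan already answers the aim with the t-test or Mann-Whitney comparison. The regression sits beneath it, and the disputed covariate is only something the analysts may add. This is fair: the three analyses are not on an equal footing, and the first two are sound. What remains is that the plan sets no formal hierarchy and does not say when the option would be used, so that choice can be made after the data are seen.

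Second, bias requires gabapentin to change non-narcotic use. The documents do not say whether such drugs are scheduled or taken as needed, and scheduled use would respond less to pain. This stands as a limit on what can be claimed, and the point is conditional for that reason.

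Third, the percentages depend on chosen inputs. The first illustration omits opioid sparing, which is perhaps the most natural reason to want this covariate. That also stands: once sparing is included, the bias can change sign or nearly cancel. The figures show that the problem is possible and can run either way; they do not estimate its size.

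Fourth, adding site to the regression is a separate matter. That is correct in so far as the concern does not depend on it. Site is nevertheless a legitimate pre-randomisation covariate, because the trial randomises by site.

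**Conclusion.** The concern holds as a conditional one. The plan permits a treatment-effect model for a stated secondary aim to be adjusted for a variable measured after randomisation and during treatment. If gabapentin changes that variable, the model does not in general estimate the total effect on narcotic use. The size cannot be derived from the documents. Under the assumed values above, the bias ranges from zero, through near-cancellation, to removal of about half or more of the effect, and it can overstate the benefit as well as understate it.

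At this sample size the problem is mainly what is being estimated, but a larger sample would not remove it. It is confined to one optional model for one secondary outcome. It should be corrected, but it does not threaten the trial's main conclusion.

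**What to change.** - Delete the sentence, or label that model exploratory and state that it does not estimate the treatment effect.
- Limit the narcotic-use regression to pre-randomisation covariates: baseline pain medication use, as planned, and site.
- Report postoperative non-narcotic use by arm as a separate descriptive outcome.
- Keep the planned t-test or Mann-Whitney comparison of narcotic use.

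The cost is one sentence deleted or relabelled, one covariate named and one descriptive line added. Nothing changes for patients. The contents of the daily medication count form are not described, so confirm that it records non-narcotic drugs; the SAP sentence already presupposes that such data will exist.
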